### 8.2 Primary Objective

Since this is a randomized trial, the two groups can be compared for CREB phosphorylation levels using a two-sample t-test. In addition to the 2-sample t-

test, descriptive statistics will be calculated for this primary outcome within each group. These statistics include n, mean, standard deviations and 95% confidence intervals.

Based on the preliminary data, the baseline level of CREB phosphorylation was 0.73 with a standard deviation of 0.26 . Using these values, we determined that there is 80% power to detect a difference of 0.21 between groups using a 2-sample t-test (alpha=0.05, 2-sided). Thus, if the control group has a value of 0.73 (based on the preliminary data) then we would be able to detect a difference if the value of CREB phosphorylation is below 0.52. Based on the preliminary data, this effect size is 0.81, and would correspond to a 29% relative change in CREB phosphorylation. This calculation is based on have 25 patients in each group being evaluable (i.e., having tumor tissue available to be evaluated). Sixty patients are to be enrolled to allow up to 10 patients (5 per group) to possibly not have evaluable tissue available at the time of analyses.

### **8.3 Secondary Objective**

There are 6 secondary objectives; each of these is focused on comparing the levels of a potential biomarker in patients. These measures are activation of ADRB2/PKA/BAD signaling pathway in the prostate glands, transcripts levels associated with ADRB2/PKA activation, plasma propranolol levels, plasma catecholamine levels, perceived stress levels, and distress levels. For each of these measures 2-sample t-tests will be calculated to compare the groups who were randomized to receive propranolol (yes/no). In addition to the 2-sample t-tests, descriptive statistics will be calculated for each measure within each group. These statistics include n, mean, standard deviations and 95% confidence intervals.

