## SCHEMA

## 1.0 Introduction and Background

Increased levels of epinephrine induced by stress inhibit apoptosis and accelerate tumor progression in mouse models of prostate cancer via  $\beta$ 2-adrenergic receptor (ADRB2)/ cAMP-dependent protein kinase (PKA)/ BCL2-associated death promoter (BAD) signaling pathway . Furthermore, analysis of 20 prostate biopsies showed significant positive correlation between increased blood epinephrine levels and activation of the ADRB2/PKA/BAD signaling pathway in the prostate gland of men . Because PKA can phosphorylate several substrates in addition to BAD, it is beneficial to analyze phosphorylation of both S75 BAD and S133 CREB to increase assay specificity. Further, antibodies to pS133CREB may be more sensitive compared to pS75 BAD-specific antibodies.

To further improve the specificity and sensitivity of measuring activation of ADRB2 signaling pathway, we have compared mRNA profiles in prostate cancer C42 cells exposed to vehicle or epinephrine using Affimetrix arrays. This comparison identified several transcripts induced by activation of ADRB2 pathway. Should the specificity of these induced transcripts be confirmed, the analysis of these transcripts in collected prostate tissues will also be conducted.

Recently, in a breast cancer mouse model, it has been shown that chronic stress promotes metastasis and that treatment with a beta-blocker can prevent metastasis . Similarly, an association between dysregulation of stress-related signaling pathways, especially the adrenergic pathway and lethal prostate cancer has been reported . These data suggest that stress and ADRB2/PKA/BAD signaling may play an important role in prostate cancer pathophysiology.

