### **2.2 Secondary Objectives**

- 2.2.1 To compare activation of ADRB2/PKA/BAD signaling pathway in the prostate glands of men two hours after taking or not taking propranolol prior to prostate biopsy or prostatectomy as indicated by phosphorylated BAD.
- 2.2.2 To determine the difference in candidate transcript levels associated with ADRB2/PKA activation between individuals two hours after taking propranolol or not taking propranolol prior to prostate biopsy or prostatectomy.
- 2.2.3 To determine plasma propranolol levels in individuals taking propranolol two hours after administration prior to prostate biopsy or prostatectomy.
- 2.2.4 To determine if plasma catecholamine levels in men with prostate cancer can be used as a biomarker to identify patients who show activation of ADRB2 signaling pathway in prostate tumors.

- 2.2.5 To determine perceived stress level differences in men with prostate cancer prior to prostate biopsy or prostatectomy to examine possible association between perceived stress level and catecholamine levels in blood and activation of ADRB2 pathway in tumors
- 2.2.6 To determine perceived distress level differences in men with prostate cancer prior to prostate biopsy or prostatectomy to examine possible association between distress level and catecholamine levels in blood and activation of ADRB2 pathway in tumors.

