#### **4.2 Methods**

#### **Compare activation of ADRB2/PKA/BAD signaling pathway in the prostate glands of men who take or do not take ADRB2-selective beta blockers**

##### **Patients scheduled for prostate biopsy.**

The research staff screens the OR and clinic schedules for potential patients and provides a list to the investigator. [name] or co-Investigator will discuss the study with the patient and inform the research nurse or coordinator (research staff) about the patients who agreed to participate in the study. Research staff will inform Tissue Procurement Lab (Director [name]; [name], Tumor Procurement Coordinator) and courier about the scheduled date and time when prostate samples will be collected.

On the day of sample collection [name] lab will prepare box with dry ice for prostate biopsy samples, a box with wet ice for blood samples as well as 2 ml cryovials (Corning, cat#430488) to collect biopsies and tubes to collect blood (Na heparin, green-capped tube, 10 ml total blood volume).

Courier will pick up boxes from Tissue Procurement Lab (Director [name]; [name], [contact]) and deliver to research staff at Charlois clinic ([name]).

Recruited patients scheduled for prostate biopsy will be randomized into two groups. Group one will receive 40 mg propranolol given by research nurse 2 hours prior to prostate biopsy. The research nurse should withhold drug and contact treating physician if SBP <120 or HR < 63. Group two will receive no treatment.

All patients will fill out stress surveys on the biopsy day.

All patients will give approximately 10 mL of blood approximately 20 min prior to prostate biopsy to test plasma catecholamine levels (collected in 10 mL green top tube (sodium heparin) and sent on ice within 1 hour to clinical lab for processing) and propranolol level (collected in 10 mL green top tube (sodium heparin) and sent on ice to The Tissue Procurement lab for processing and storage as described below). For group one that takes propranolol, this blood sample will be drawn at 1.5 -2 hours after taking the propranolol tablet.

For the biopsy, at least 1 core of the prostate specimen is to be flash frozen (on dry ice -80C) for laboratory analysis. Each biopsy sample will be collected into separate cryovials. The samples will be picked up by courier at Charlois clinic and delivered to Tissue Procurement laboratory.. The tissue samples will be frozen at -80 C.

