### **Patients scheduled for prostatectomy.**

Research staff will inform Tissue Procurement Lab (Director [name]; [name], Tumor Procurement Coordinator) about the scheduled date and time when samples from prostate cancer patients will be collected at OR. Prior to the day of sample collection at specified time [name] lab will provide vials and freezing media to collect prostatectomy samples and plasma samples (Na heparin, green cup).

Recruited patients scheduled for prostatectomy will be randomized into two groups. Group one will receive 40 mg propranolol given by research staff 2 hours prior to prostatectomy. The research staff should withhold drug and contact the study physician performing the procedure and/or the anesthesiologist if SBP <120 or HR < 63. Group two will receive no treatment. All patients will fill out stress surveys prior to prostatectomy.

Research staff will collect stress questionnaire and will collect blood into the vials with Na heparin that will be stored on ice (+4C). All patients will give approximately 10 ml of blood approximately 20 min prior to prostatectomy to test plasma catecholamine levels and propranolol level. For group one that takes propranolol, this blood sample will be drawn at 1.5 -2 hours after taking the propranolol tablet. Blood will be collected into two 10 mL green top (sodium heparin) tubes. One tube will sent on ice within 1 hour to the clinical lab for processing of fractionated catecholamines. The other tube will be sent on ice to The Tissue Procurement lab for processing and storage. The plasma will be separated, transferred to cryovials, and stored in -80C at the Tissue Procurement Lab

Prior to anesthesia patient will be evaluated by anesthesiologist for hypotension and bradycardia. Prostatectomy samples will be collected by Tissue Procurement Coordinator and placed into cryovials and flash-frozen. At least 3 vials with the prostate specimens will be flash frozen (on dry ice -80C) for laboratory analysis and stored at the Tissue Procurement Lab.

Prostate samples will be analyzed for the overall status of prostate tissue (by pathologist) and for activation of ADRB2/PKA signaling pathway .

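### The arm-versus-arm t-tests in Section 8.3 do not address objective 2.2.4 or the association parts of objectives 2.2.5 and 2.2.6

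*Combined protocol and SAP*

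**What the plan says.** Section 8.3 says of the six secondary objectives that "each of these is focused on comparing the levels of a potential biomarker in patients". It lists the measures (pathway activation, transcripts, plasma propranolol, plasma catecholamines, perceived stress, distress) and continues: "For each of these measures 2-sample t-tests will be calculated to compare the groups who were randomized to receive propranolol (yes/no". The only other output is a summary of each measure separately within each arm: n, mean, standard deviation and 95% confidence interval.

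Section 2.2 asks for something different in three places:

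- **2.2.4:** whether plasma catecholamines in men with prostate cancer "can be used as a biomarker to identify patients who show activation of ADRB2 signaling pathway in prostate tumors".
- **2.2.5:** differences in perceived stress, and also "to examine possible association between perceived stress level and catecholamine levels in blood and activation of ADRB2 pathway in tumors".
- **2.2.6:** differences in distress, and also "to examine possible association between distress level and catecholamine levels in blood and activation of ADRB2 pathway in tumors".

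The data for these questions will exist. Section 4.2 has catecholamines measured and both questionnaires completed in all patients, and it expresses CREB and BAD phosphorylation as ratios of phosphorylated to total protein in the tissue samples.

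**The concern.** Objective 2.2.4 and the second halves of 2.2.5 and 2.2.6 each relate two measurements taken in the same man. If Section 8.3 is followed as written, the report will show whether mean catecholamines, stress and distress differ by arm. It will not show whether men with higher epinephrine have higher pCREB ratios.

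Two things are at stake. An arm t-test on catecholamines could be taken as evidence for or against the biomarker, which it is not. And if the real question is analysed later, the analyte, its scale, the handling of arm and the meaning of activation would all be chosen with the data in view. The plan's own rationale is an association: Section 1.0 cites, from 20 biopsies, a "significant positive correlation between increased blood epinephrine levels and activation of the ADRB2/PKA/BAD signaling pathway in the prostate gland of men".

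**Working it through.** **1. What the planned test estimates.** For epinephrine E, the two-sample statistic is t = (mean E in Group 1 − mean E in Group 2) / [s_E × √(1/n1 + 1/n2)]. The pCREB ratio does not appear in it. Shuffle the pCREB values among men within an arm and t is unchanged, while the epinephrine–pCREB correlation can take very different values. Running the t-test on pCREB as well gives a second marginal difference, still not the relation between the two. The same holds for stress and distress.

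**2. Whether another section fills the gap.**
- Sections 8.1 and 8.2 cover only the primary outcome.
- The close of the laboratory plan in Section 4.2 says the results will inform whether an epinephrine level for activation can be found. It gives no model or test.
- Section 8.4 uses epinephrine above 1 nM only as an interim trigger in treated men, and says the interim look has no statistical testing.

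**3. The plan's own figure.** Inputs from Section 8.1: difference 0.21, SD 0.26, 25 evaluable per group, two-sided alpha 0.05. The effect size is 0.21/0.26 = 0.808, and the noncentral t gives power of 79.9% against the stated 80%. The primary sizing reproduces. No sizing is stated for the associations.

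**4. What an association analysis could deliver.** By Fisher's z, with k covariates, the detectable r at 80% power is tanh[(1.960 + 0.842)/√(n − 3 − k)].

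| Men | k | Calculation | Detectable r |
|---|---|---|---|
| 25 evaluable controls | 0 | tanh(2.802/√22) | 0.54 |
| 25, procedure term | 1 | tanh(2.802/√21) | 0.55 |
| 50 evaluable | 0 | tanh(2.802/√47) | 0.39 |
| 50, arm and procedure | 2 | tanh(2.802/√45) | 0.40 |

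An observed r of 0.5 (assumed, for illustration) has 95% CI tanh(0.549 ± 1.960/√22) = 0.13 to 0.75 with 25 men, and tanh(0.549 ± 1.960/√47) = 0.26 to 0.68 with 50.

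**5. What a cut-off could deliver.** Take an assumed AUC of A = 0.70 and the Hanley–McNeil variance [A(1−A) + (n1−1)(Q1−A²) + (n0−1)(Q2−A²)]/(n1·n0), with Q1 = A/(2−A) = 0.538 and Q2 = 2A²/(1+A) = 0.576.
- 10 activated of 50 (the expectation in Section 4.2, item 3): SE 0.100, 95% CI 0.50 to 0.90.
- 5 of 25 controls (assuming the same 20%): SE 0.143, 95% CI 0.42 to 0.98.

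The 10 of 50 is optimistic, because item 3 also expects no phosphorylation in men given propranolol.

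**6. Features the model must respect.**
- Group 1 blood is drawn 1.5 to 2 hours after dosing, and propranolol is expected to block the pathway. Pooling arms without allowing for this could mask or distort the relation.
- Sampling differs by procedure: for biopsy, "at least 1 core of the prostate specimen is to be flash frozen"; for prostatectomy, "At least 3 vials with the prostate specimens will be flash frozen".
- Objectives 2.2.4 to 2.2.6 concern men with prostate cancer, but Section 3.1 requires only a scheduled biopsy or prostatectomy.

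**The case against.** The strongest reply is that this is a self-described pilot, that the objectives speak only of possible associations, and that with 25 controls little can be learned. That supports an exploratory label and modest expectations. It does not supply a method for a stated objective, and an imprecise estimate with an interval still addresses the question, which the arm t-test does not.

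It can also be said that much of a detailed fix is preference: a named correlation or regression with arm handling stated would close the gap. That is fair. The essential parts are the pairing of measures, the population, and the handling of arm and procedure. The amendment might also say whether the mRNA signature, which Section 4.2 names as the second method of assessing activation, will be used here.

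A reader might infer that 2.2.4 has no planned analysis at all, or that 2.2.5 and 2.2.6 are wholly neglected. The documents do not support that. Catecholamines do receive a t-test and descriptives, and the difference wording in 2.2.5 and 2.2.6 can be read as covered by the arm comparisons.

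Nor can it be claimed that activation is undefined everywhere. Section 4.2 cites an earlier pilot study, and the worksheet contents in Appendices J to M are not visible in the text. Survey timing, which differs between Section 7.2 and Appendix N, is a separate matter and adds nothing to this point.

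**Conclusion.** The point holds in limited form. Section 8.3 as written produces results that do not answer 2.2.4 or the association parts of 2.2.5 and 2.2.6, and no visible section provides a method that would. This rests on the text and needs no numerical assumption. It should be corrected before analysis, but it touches secondary objectives only: the primary comparison, its 80% power and patient safety stand.

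The detectable correlations of about 0.54 (25 controls) and 0.39 (50 evaluable men) assume roughly bivariate normal data, full evaluability as planned and no multiplicity adjustment. The normal model does not represent a 20% activated subgroup.

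Two further inferences should be resisted. The significant correlation in 20 biopsies does not supply an effect size: under an assumed Pearson test at two-sided 5%, it would only imply an observed |r| of at least 0.44, which is not an estimate of the true value. And the survey–catecholamine pairs should not be sized on all 60 enrolled men just because they need no tissue. Some biopsy patients may prove not to have cancer and so fall outside the objectives, and Section 3.0 allows recruitment beyond 60.

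**What to change.** Amend Section 8.3 as follows.

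- **(a) Objective 2.2.4.** Regress the continuous pCREB ratio (pBAD ratio secondary) on plasma epinephrine, named in advance as lead analyte with its scale fixed. The main fit is in evaluable Group 2 men with prostate cancer, with a term for biopsy or prostatectomy. Report the slope or partial correlation with a 95% CI. Any model in both arms must include arm, let the slope differ by arm, and be labelled supportive.
- **(b) Objectives 2.2.5 and 2.2.6.** Estimate the association of stress and of distress with epinephrine, adjusted for arm and procedure, and with the pCREB and pBAD ratios, in Group 2 or in both arms with arm handled as in (a). Label these exploratory. State whether men found not to have cancer are included.
- **(c) Cut-offs.** Treat any ROC or threshold summary as exploratory, with activation defined before analysis.
- **(d) The arm t-tests.** Keep them as arm comparisons, and state that they do not answer 2.2.4 or the association questions.

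The cost is a reworded section and a few lines of code on data already being collected, with no added patients or samples. The downside is wide intervals, one or two degrees of freedom for arm and procedure (another for the slope difference in the supportive model), and a few more exploratory estimates to report as such.

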### 7.2 Secondary Outcomes

- 7.2.1 BAD phosphorylation by western blot in prostate tissue from men two hours after taking or not taking propranolol prior to prostate biopsy
- 7.2.2 Difference in levels of transcripts that reflect ADRB2/PKA activation as measured by real-time PCR in prostate tissue from men two hours after taking or not taking propranolol prior to prostate biopsy or prostatectomy.
- 7.2.3 Plasma propranolol levels as measured by fluorometric detection from men two hours after taking or not taking propranolol prior to prostate biopsy or prostatectomy.
- 7.2.4 Plasma catecholamine levels (including epinephrine) measured by ELISA from men two hours after taking or not taking propranolol prior to prostate biopsy or prostatectomy.
- 7.2.5 Self-perceived stress as measured by The Perceived Stress Questionnaire (Appendix C) from men on the day of surgery before taking propranolol, prior to prostate biopsy or prostatectomy.
- 7.2.6 Distress score as measured by The Distress Thermometer (Appendix D) from men on the day of surgery before taking propranolol, prior to prostate biopsy or prostatectomy.

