**Questions**

1. In the last 2 weeks, how often have you felt that you were unable to control the important things in your life?  
0 = Never  
1 = Almost Never  
2 = Sometimes  
3 = Fairly Often  
4 = Very Often
  
2. In the last 2 weeks, how often have you felt confident about your ability to handle your personal problems?  
0 = Never  
1 = Almost Never  
2 = Sometimes  
3 = Fairly Often  
4 = Very Often
  
3. In the last 2 weeks, how often have you felt that things were going your way?  
0 = Never  
1 = Almost Never  
2 = Sometimes  
3 = Fairly Often  
4 = Very Often
  
4. In the last 2 weeks, how often have you felt difficulties were piling up so high that you could not overcome them?  
0 = Never  
1 = Almost Never  
2 = Sometimes  
3 = Fairly Often  
4 = Very Often

\*Modified from:

Evaluating the effect of ADRB2 blockers on PKA/BAD/CREB signaling in the prostate  
gland

[figure not shown]
Wake Forest Baptist Comprehensive Cancer Center (WFBCCC)  
WFBCCC # 85716

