## Appendix D – Distress Thermometer

WISER PID: \_\_\_\_\_ Date Completed: \_\_\_\_ / \_\_\_\_ / \_\_\_\_

PI: [name]., [name], D.V.M., Ph.D.

Study Number: 8 5 7 1 6

NCCN DISTRESS THERMOMETER
 
Instructions: Please circle the number (0–10) that best describes how much distress you have been experiencing in the past week including today.
 
Extreme distress
 		
NCCN National Comprehensive Cancer Network®
 
NCCN Distress Thermometer and Problem List for Patients
 
PROBLEM LIST Please indicate if any of the following has been a problem for you in the past week including today.
 
Be sure to check YES or NO for each.
 

YES	NO	Practical Problems	YES	NO	Physical Problems	

		Child care			Appearance	

		Housing			Bathing/dressing	

		Insurance/financial			Breathing	

		Transportation			Changes in urination	

		Work/school			Constipation	

		Treatment decisions			Diarrhea	

					Eating	

					Fatigue	

					Feeling swollen	

					Fever	

					Getting around	

					Indigestion	

					Memory/concentration	

					Mouth sores	

					Nausea	

					Nose dry/congested	

					Pain	

					Sexual	

					Skin dry/itchy	

					Sleep	

					Substance abuse	

					Tingling in hands/feet	

 
Family Problems
 

 Dealing with children

 Dealing with partner

 Ability to have children

 Family health issues

 
Emotional Problems
 

 Depression

 Fears

 Nervousness

 Sadness

 Worry

 Loss of interest in usual activities

 Spiritual/religious concerns

 
Other Problems: _____
	YES	NO	Practical Problems	YES	NO	Physical Problems			Child care			Appearance			Housing			Bathing/dressing			Insurance/financial			Breathing			Transportation			Changes in urination			Work/school			Constipation			Treatment decisions			Diarrhea						Eating						Fatigue						Feeling swollen						Fever						Getting around						Indigestion						Memory/concentration						Mouth sores						Nausea						Nose dry/congested						Pain						Sexual						Skin dry/itchy						Sleep						Substance abuse						Tingling in hands/feet

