#### Post-randomization Activities (1-2hr Post-Drug if randomized to Group 1)

Blood Draw:  Yes  No Time \_\_\_\_\_ Initials \_\_\_\_\_

Perceived Stress Survey:  Yes  No Time: \_\_\_\_\_ Initials \_\_\_\_\_  
Score \_\_\_\_\_

Distress Thermometer Survey:  Yes  No Time \_\_\_\_\_ Initials \_\_\_\_\_  
Score \_\_\_\_\_

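### Section 8.3 t-tests stress and distress between arms although 7.2.5 and 7.2.6 record both before the drug, and it omits the association analysis that objectives 2.2.5 and 2.2.6 ask for

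*Combined protocol and SAP*

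**What the plan says.** Section 8.3 treats all six secondary objectives as comparisons of biomarker levels. The last four measures in its list are "plasma propranolol levels, plasma catecholamine levels, perceived stress levels, and distress levels". The instruction that follows makes no exception: "For each of these measures 2-sample t-tests will be calculated to compare the groups who were randomized to receive propranolol (yes/no". The only other output planned is descriptive statistics within each group.

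Section 7.2 fixes the time of the two questionnaire outcomes:

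- 7.2.5: "Self-perceived stress as measured by The Perceived Stress Questionnaire (Appendix C) from men on the day of surgery before taking propranolol".
- 7.2.6: "Distress score as measured by The Distress Thermometer (Appendix D) from men on the day of surgery before taking propranolol".

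Outcomes 7.2.1 to 7.2.4 are instead defined at two hours after taking or not taking the drug. The protocol therefore separates pre-drug from post-drug measures.

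The forms look backwards. The first item in Appendix C reads "In the last 2 weeks, how often have you felt that you were unable to control the important things in your life", and Appendix D asks "how much distress you have been experiencing in the past week including today".

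Appendix N gives a different time. It lists both surveys, together with the blood draw, under the heading "Post-randomization Activities (1-2hr Post-Drug if randomized to Group 1".

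Objectives 2.2.5 and 2.2.6 state the purpose of the scores: to examine a possible association with blood catecholamines and with activation of the ADRB2 pathway in tumors.

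**The concern.** A score taken before a drug is given cannot be changed by that drug. If Section 7.2 describes what happens, the two t-tests compare the arms on something propranolol has not yet had a chance to affect. A p-value below 0.05 could then be taken for a propranolol effect on stress, and one above 0.05 for evidence of no effect. The data would support neither statement.

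The tests would also stand in for an analysis the trial does want. The objectives ask whether more stressed men have higher catecholamines and more pathway activation. A comparison of mean stress between arms says nothing about that. Two of the six secondary objectives would be closed with a test that does not address them.

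**Working it through.** **1. The plan's own figure.** The plan gives no figure for the stress or distress tests. Its only power figure, in Section 8.1, is for the primary outcome: difference 0.21, SD 0.26, 25 per group, two-sided alpha 0.05. The effect size is 0.21 / 0.26 = 0.81. Power is 79.9% for the t-test (81.5% by the normal approximation), so the stated 80% reproduces. This matters here only as the source of the 5% level. Section 8.3 states no alpha, so 0.05 two-sided is an assumption for the secondary tests.

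**2. When the surveys are completed.**

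| Place | Order of survey and drug |
|---|---|
| 7.2.5, 7.2.6 | Survey before drug |
| 4.2, laboratory experimental plan, step 2 | Surveys listed before drug |
| 4.2, biopsy patients | On the day; order not given |
| 4.2, prostatectomy patients | Before surgery; order not given |
| Appendix N | 1 to 2 hours after drug in Group 1 |

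The outcome definitions and the laboratory plan agree. The worksheet on which the day's activities are recorded contradicts them.

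**3. Pre-drug timing (Section 7.2).** The drug effect on each score is zero. If the answers are also unaffected by knowing the arm, the null hypothesis holds for both tests:

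- Each test: probability of p < 0.05 is 0.05.
- At least one of two, independent: 1 − (1 − 0.05)² = 1 − 0.9025 = 0.0975.
- At least one of two, correlated scores (100,000 simulated null trials, 30 against 30):

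| Correlation | 0 | 0.3 | 0.6 | 0.9 |
|---|---|---|---|---|
| Probability | 0.097 | 0.096 | 0.087 | 0.072 |

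Both scores come from the same man on the same day, so some correlation is likely and 9.75% is the top of the range.

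**4. Post-drug timing (Appendix N).** The null is no longer guaranteed. With 30 per arm, power would be 12%, 48% and 86% for assumed true standardized differences of 0.2, 0.5 and 0.8. These differences are illustrative; the documents give none for either score. The test would then have some power, but for an outcome other than the one 7.2.5 and 7.2.6 define.

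**5. Match to the objectives.** Objectives 2.2.1 and 2.2.2 name the contrast between taking and not taking propranolol. Objectives 2.2.5 and 2.2.6 name no arms; they name catecholamines and pathway activation. Section 8.3 contains no correlation or regression. The mismatch holds under step 3 and step 4 alike.

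**The case against.** The strongest objection is that the timing is not settled. Appendix N is the form staff complete on the day, and its layout puts the surveys after the drug. Section 1.0 cites a randomized study in which a 20 mg oral dose reduced anxiety in surgery patients, and the distress item includes the current day. If the worksheet governs, a drug effect on distress is possible and a between-arm test is not empty. This stands, and it limits the conclusion in step 3 to the Section 7.2 timing. The one-week and two-week recall periods make a large effect of one dose less likely but do not exclude it.

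A reader might also infer that, on the Section 7.2 timing, any significant result must be chance. The documents do not support that. Assignment is made at registration, before treatment (Section 4.1), and the control arm receives no treatment, with no placebo described (Section 4.2). Men may know their arm when they answer, and that knowledge could shift the scores. Such a shift would be an effect of knowing the assignment, not of propranolol. It makes the test harder to interpret and does not rescue it as a drug comparison.

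Two smaller points are fair. Nothing in the plan says these tests will be reported as propranolol effects, so the risk of misreading is a risk only. The opening words of 2.2.5 and 2.2.6 do speak of differences in stress and distress levels; but they do not say between arms, and their stated purpose is association.

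**Conclusion.** The point holds in a conditional form. On the timing in 7.2.5 and 7.2.6, the between-arm t-tests of stress and distress cannot show a propranolol effect. If knowledge of the arm also leaves the answers unchanged, they carry only a false-positive rate of 5% each, and between about 7.2% and 9.75% for at least one across the correlations examined. These figures assume a two-sided alpha of 0.05 for the secondary tests.

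On the Appendix N timing the tests could detect something, but they would depart from the defined outcome and could not separate the drug from knowledge of the arm.

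On either timing they leave objectives 2.2.5 and 2.2.6 unanswered, which is the more consequential part. The plan should be changed. The primary comparison, the sample size and the safety rules are not affected.

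**What to change.** 1. Reconcile Appendix N with 7.2.5 and 7.2.6 so that one survey time, relative to the drug, applies throughout, and state it in Section 4.2, where the biopsy and prostatectomy paragraphs leave it open. Appendix N has time fields for the drug and for each survey, so the actual order can be checked for any man already enrolled.
2. In Section 8.3, remove perceived stress and distress from the between-arm t-tests. Report the pre-drug scores by arm descriptively, without p-values, and state that no drug effect on either score is estimated.
3. In their place, pre-specify a correlation or regression of each score with plasma catecholamines and with pCREB and pBAD. The catecholamines and tissue markers are measured after dosing in Group 1, so these analyses should adjust for arm.

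The cost is a few sentences, one form heading and a small amount of extra analysis. No new patients, visits or samples are needed. Steps 1 and 3 should accompany step 2: deleting the tests alone would leave the two objectives with descriptive statistics only.
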